AST (SGOT) and ALT (SGPT)	$\leq 2.5 \times \text{ULN}$ ($\leq 5 \times \text{ULN}$ for participants with liver metastases)
Coagulation	
International normalized ratio (INR) OR prothrombin time (PT)	$\leq 1.5 \times \text{ULN}$ unless participant is receiving anticoagulant therapy as long as PT or aPTT is within therapeutic range of intended use of anticoagulants
Activated partial thromboplastin time (aPTT)	
ALT (SGPT)=alanine aminotransferase (serum glutamic pyruvic transaminase);	
AST (SGOT)=aspartate aminotransferase (serum glutamic oxaloacetic transaminase);	
GFR=glomerular filtration rate; ULN=upper limit of normal.	

^a Criteria must be met without erythropoietin dependency and without packed red blood cell (pRBC) transfusion within last 2 weeks.

^b Creatinine clearance (CrCl) should be calculated per institutional standard.

Note: This table includes eligibility-defining laboratory value requirements for treatment; laboratory value requirements should be adapted according to local regulations and guidelines for the administration of specific chemotherapies.

Women of child-bearing potential (WOCBP) must not be breastfeeding and must have a negative pregnancy test within 3 days prior to initiation of dosing. She must agree to use an acceptable method of birth control from the time of the negative pregnancy test up to 120 days after the last dose of study drug. WOCBP must agree to adhere to the contraceptive guidance in Appendix 5.

Note: A female participant is eligible to participate if she is not a woman of childbearing potential as defined in Appendix 5.

Fertile men must agree to use an acceptable method of birth control as described in Appendix 5 while on study drug and up to 120 days after the last dose of study drug and also refrain from donating sperm during this period.

All associated toxicity from previous or concurrent cancer therapy must be resolved (to \leq Grade 1 or Baseline) prior to study treatment administration, unless stable status as assessed by investigator e.g. hypothyroidism, adrenal insufficiency, or other. Steroids for physiological replacement are allowed.

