5.2 EXCLUSION CRITERIA

1. Patients with clinical or radiographic evidence of leptomeningeal disease.
2. Those who experienced grade 3 or 4 neurotoxicity from prior SRS.
3. Contraindications to MRI (implanted metal device or foreign bodies) or MRI contrast (insufficient renal function or allergy).
4. Subjects with major medical, neurologic or psychiatric condition who are judged as unable to fully comply with study therapy or assessments should not be enrolled.
5. Active secondary malignancy unless the malignancy is not expected to interfere with the evaluation of safety and is approved by the PI. Examples of the latter include basal or squamous cell carcinoma of the skin, in-situ carcinoma of the cervix, and isolated elevation of prostate-specific antigen. Subjects with a completely treated prior malignancy and no evidence of disease for \geq 2 years are eligible.
6. Has a known history of or is positive for hepatitis B (hepatitis B surface antigen [HBsAg] reactive) or known active hepatitis C virus infection (note treated and cured history of hepatitis C is allowed)(hepatitis C virus [HCV] RNA [qualitative] is detected). Note: Without known history, testing needs to be performed to determine eligibility. Hepatitis C antibody (Ab) testing is allowed for screening purposes.
7. Has a known history of human immunodeficiency virus (HIV) infection. No HIV testing is required unless mandated by local health authority.
8. The use of corticosteroids is not allowed for 10 days prior to initiation of therapy (based upon 5 times the expected half-life of dexamethasone) except patients who are taking steroids for physiological replacement. If alternative corticosteroid therapy has been used, consultation with the PI is required to determine the washout period prior to initiating study treatment.

9. Subjects with a condition requiring systemic treatment with either corticosteroids (> 10 mg daily prednisone equivalent) or other immunosuppressive medications within 14 days of study initiation. Inhaled or topical steroids, and adrenal replacement steroid doses > 10 mg daily prednisone equivalent, are permitted in the absence of active autoimmune disease.
10. Major surgical procedure, open biopsy (excluding skin cancer resection), or significant traumatic injury within 14 days of initiating study drug (unless the wound has healed) or anticipation of the need for major surgery during the study.
11. Non-healing wound, ulcer, or bone fracture.

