The recommendations for irAE management, in accordance with the joint American Society of Clinical Oncology Clinical Practice Guidelines (Brahmer, 2018) and National Comprehensive Cancer Network (NCCN Guidelines®), are listed in Appendix 6.

Treatment of irAEs is mainly dependent upon severity as defined by NCI-CTCAE v5.0. In general, management by CTCAE v5.0 grading, as per ASCO, is listed below:

- Grade 1: study treatment should be continued with close monitoring, with the exception of some neurologic, hematologic, and cardiac toxicities.
- Grade 2: study treatment may be suspended for most Grade 2 toxicities, with consideration of resuming when symptoms revert to Grade 1 or less. Corticosteroids may be administered (initial dose of 0.5 to 1 mg/kg/day of prednisone or equivalent).
- Grade 3: study treatment is generally suspended and the high-dose corticosteroids (prednisone 1 to 2 mg/kg/day or methylprednisolone 1 to 2 mg/kg/day) treatment should be initiated. Corticosteroids should be tapered over the course of at least 4 to 6 weeks. Some refractory cases may require infliximab or other immunosuppressive therapy.
- Grade 4: in general, permanent discontinuation of study treatment is recommended, with the exception of endocrinopathies that have been controlled by hormone replacement.

For organ/system specific management guidelines, review ASCO guideline tables in Appendix 7.

Since inhibition of PD-L1 stimulates the immune system, irAEs may occur. Treatment of irAEs is mainly dependent upon severity (NCI-CTCAE grade):

- Grade 1 to 2: treat symptomatically or with moderate dose steroids, more frequent monitoring
- Grade 1 to 2 (persistent): manage similar to high grade AE (Grade 3 to 4)
- Grade 3 to 4: treat with high dose corticosteroids

Anemia

Anemia is considered a important identified risk based on toxicological findings with Bintrafusp Alfa (M7824) in cynomolgus monkey indicating a decrease in Hgb, RBCs, and hematocrit that was fully reversible or showed a substantial trend toward recovery. Notably, there are many reasons for anemia in patients with advanced cancer, which is why a thorough investigation of new anemia cases of unspecified etiology is requested.

Risk management measures in addition to routine laboratory tests will include:

- Subjects must enter the study with Hgb values at least 9 g/dL, independent of recent (≤ 14 days) packed red blood cell transfusion and/or use of an erythropoietin-stimulating agent.

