6.2.6 CONCOMITANT AND EXCLUDED THERAPIES

Steroids are allowed to manage AEs as described in protocol. Medications or vaccinations specifically prohibited in the exclusion criteria (See section 5.2) are not allowed during the ongoing trial. The following are also prohibited and are not allowed:

- Any traditional Chinese medication used as anticancer treatment (regardless of the type of cancer) is prohibited. Traditional Chinese medication for indications other than anticancer treatment, such as supportive care, may be administered at the discretion of the Investigator.
- Herbal remedies with immunostimulating properties (e.g., mistletoe extract) or known to potentially interfere with major organ function (e.g., hypericin).

If there is a clinical indication for any medication or vaccination specifically prohibited during the trial, discontinuation from trial therapy or vaccination may be required. The final decision on any supportive therapy or vaccination rests with the principal investigator and/or the subject's primary physician. However, the decision to continue the subject on trial therapy or vaccination schedule requires the mutual agreement of the principal investigator, and the subject.

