 - For **Grade 3 or 4 diarrhea/colitis**, treat with intravenous steroids followed by high dose oral steroids.
 - When symptoms improve to Grade 1 or less, steroid taper should be started and continued over no less than 4 weeks.
- **Type 1 diabetes mellitus** (if new onset, including diabetic ketoacidosis [DKA]) or \geq Grade 3 Hyperglycemia, if associated with ketosis (ketonuria) or metabolic acidosis (DKA)
 - For **T1DM or Grade 3-4 Hyperglycemia**
 - Insulin replacement therapy is recommended for Type I diabetes mellitus and for Grade 3-4 hyperglycemia associated with metabolic acidosis or ketonuria.
 - Evaluate patients with serum glucose and a metabolic panel, urine ketones, glycosylated hemoglobin, and C-peptide.
- **Hypophysitis:**
 - For **Grade 2** events, treat with corticosteroids. When symptoms improve to Grade 1 or less, steroid taper should be started and continued over no less than 4 weeks. Replacement of appropriate hormones may be required as the steroid dose is tapered.
 - For **Grade 3-4** events, treat with an initial dose of IV corticosteroids followed by oral corticosteroids. When symptoms improve to Grade 1 or less, steroid taper should be started and continued over no less than 4 weeks. Replacement of appropriate hormones may be required as the steroid dose is tapered.
- **Hyperthyroidism or Hypothyroidism:**

Thyroid disorders can occur at any time during treatment. Monitor patients for changes in thyroid function (at the start of treatment, periodically during treatment, and as indicated based on clinical evaluation) and for clinical signs and symptoms of thyroid disorders.

- **Grade 2** hyperthyroidism events (and **Grade 2-4** hypothyroidism):
 - In hyperthyroidism, non-selective beta-blockers (e.g. propranolol) are suggested as initial therapy.
 - In hypothyroidism, thyroid hormone replacement therapy, with levothyroxine or liothyroinine, is indicated per standard of care.
- **Grade 3-4** hyperthyroidism

- Treat with an initial dose of IV corticosteroid followed by oral corticosteroids. When symptoms improve to Grade 1 or less, steroid taper should be started and continued over no less than 4 weeks. Replacement of appropriate hormones may be required as the steroid dose is tapered.
- **Hepatic:**
 - For **Grade 2** events, monitor liver function tests more frequently until returned to baseline values (consider weekly).
 - Treat with IV or oral corticosteroids

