Appendix 1: immunotherapy Response Assessment for Neuro-Oncology (iRANO)

Modified Excerpt from Original Publication

Selected sections from the immunotherapy Response Assessment for Neuro-Oncology (iRANO), are presented below.

For the purposes of the current study, we will use a modified version of iRANO (modified iRANO) that allows intracranial tumors that are >0.5 and <1.0 cm assessed by MRI to be considered measurable disease. This will be the only modification.

iRANO Criteria

Proprietary Information of MD Anderson

The iRANO guidelines incorporate criteria previously defined by the RANO working committee to define complete response, partial response, minor response, stable disease, progressive disease, and non-evaluable disease for patients with malignant glioma,¹⁶ low-grade glioma,⁴⁰ and brain metastases.¹⁸ The key component of the iRANO criteria is specific additional guidance for the determination of progressive disease in patients with neuro-oncological malignancies undergoing immuno- therapy (table 1, figure 3). Specifically, the iRANO criteria advocate for the confirmation of radiographic progression in appropriate patients defined by clinical status and time from initiation of immunotherapy.

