In patients who have imaging findings that meet RANO criteria for progressive disease^{16–18} within 6 months of starting immunotherapy including the development of new lesions, confirmation of radiographic progression on follow-up imaging before defining the patient as non- responsive to treatment might be needed provided that the patient does not have new or substantially worse neurological deficits. Such patients might be allowed a window of 3 months before confirming disease progression with the scan that first showed initial progressive changes as the new reference scan for comparison with subsequent imaging studies. If RANO criteria for progressive disease are met on the follow-up scan 3 months later, non-responsiveness to treatment should be assumed, and the date of progressive disease should be back-dated to the initial date when it was first identified (table 1). Patients who develop substantial new or worsened neurological deficits not due to comorbid events or a change in co-administered medication at any time within the 3-month follow-up window should be designated as non-responsive to treatment and should discontinue immunotherapy. For these patients, the date of actual tumor progression should also be back-dated to the date when radiographic progressive disease was initially identified.

RANO and iRANO criteria (Brain Metastases)

	Brain metastases
COMPLETE TARGET	Disappearance of all enhancing target and non-lesions for ≥ 4 weeks; no new lesions; no steroids; clinically stable or improved
PARTIAL RESPONSE	$\geq 30\%$ decrease in sum of longest diameters of target lesions for ≥ 4 weeks; no new lesions; stable or decreased steroid dose; clinically stable or improved
MINOR RESPONSE	NA
STABLE DISEASE	Does not qualify for complete response, partial response, or progressive disease

Proprietary Information of MD Anderson

PROGRESSIVE DISEASE	$\geq 20\%$ increase in the sum of longest diameters of target lesions; or unequivocal progression of enhancing non-target lesions; or new lesions; or substantial clinical decline
----------------------------	---

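### Appendix 1 counts every steroid against RANO-BM/iRANO brain response and sets no reference dose, so the CR rate, and to a lesser extent the response rate, can be understated

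*Combined protocol and SAP*

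**What the plan says.** Section 4.2 lists intracranial objective response rate as a secondary objective, measured by RANO-BM, iRANO and RECIST 1.1. Section 9.3 has a subsection on extracranial response rate but none on intracranial response. For RANO-BM and iRANO, the brain metastases table in Appendix 1 is therefore the operative rule.

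That table sets these steroid conditions:
- CR: "no new lesions; no steroids; clinically stable or improved"
- PR: "no new lesions; stable or decreased steroid dose; clinically stable or improved"

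Both responses must hold for at least 4 weeks. Appendix 1 changes the published criteria only in the lesion size that counts as measurable, and adds: "This will be the only modification".

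Elsewhere the protocol expects steroid use that has nothing to do with the brain:
- Section 5.1 names adrenal insufficiency among the stable toxicities acceptable at entry and says: "Steroids for physiological replacement are allowed".
- Exclusion 8 in Section 5.2 bars recent corticosteroids, "except patients who are taking steroids for physiological replacement".
- Section 6.2.6: "Steroids are allowed to manage AEs as described in protocol".
- Section 6.2.3, for Grade 3 immune-related events: "Corticosteroids should be tapered over the course of at least 4 to 6 weeks".
- Section 8.11, on hypophysitis: "Replacement of appropriate hormones may be required as the steroid dose is tapered".

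**The concern.** The steroid clause in the response table is there to stop a steroid effect on the brain from being read as a drug response. As printed, it also catches hormone replacement and steroids given for lung, bowel, liver or kidney events. Part of any gap between the RECIST 1.1 rate and the RANO-BM/iRANO rates would then reflect endocrine status and extracranial toxicity, not the brain lesions.

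The situation is likely to arise. Melanoma and NSCLC patients, 20 of the 30 planned at the recommended dose, must have had prior PD-1 based therapy, and stable adrenal insufficiency does not exclude them.

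The plan is also uneven on cause. For progression, Appendix 1 sets aside neurological deficits explained by comorbid events or changes in other medication. Section 9.3.7 confines its steroid reporting to symptom management. Only the CR and PR steroid clause ignores the reason for the drug. Section 8.8 has scans assessed locally in an open-label trial, so assessors could apply an undefined reference dose differently.

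**Working it through.** The plan gives no target, power or expected steroid use for intracranial response, so there is no figure of its own to reproduce. The denominator is consistent: 6 + 24 = 30 patients at the recommended dose (Section 9.2).

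**Step 1. Apply the table as a decision rule.** CR if all lesions are gone and the current steroid dose is zero. PR if shrinkage is at least 30% and the current dose is no higher than the reference. Appendix 1 does not define the reference; baseline is assumed here.

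| Steroid situation at scoring | Lesions gone | Shrinkage of 30% or more |
|---|---|---|
| None | CR | PR |
| Replacement since baseline, unchanged | PR | PR |
| Replacement started on study | not a responder | not a responder |
| Immune-event course, dose above baseline | not a responder | not a responder |
| Immune-event course tapered to zero | CR | PR |
| Baseline replacement, immune-event course tapered back to replacement | PR | PR |

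If the previous visit is the reference instead, newly started replacement at a constant dose becomes PR, and a dose being tapered counts as decreased. The undefined reference therefore changes who is a responder.

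**Step 2. Check the timing.** The Table 3 footnote has brain MRI every 4 weeks for 16 weeks and every 8 weeks after that. Section 8.1.4 has every 4 weeks for 12 weeks, then every 8, then every 12 after the first year. Steroid tapers run at least 4 weeks (Section 8.11) or at least 4 to 6 weeks (Section 6.2.3). A raised-dose period can therefore cover one or more response scans. A response that outlasts it can still be scored afterwards.

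**Step 3. Illustrate the size.** Observed response rate = p × (1 − s × m), so the loss is p × s × m. All three inputs are assumptions:
- p, true response rate: 0.20 to 0.50.
- s, share of radiographic responders whose dose goes above baseline: 0.10 to 0.30.
- m, share of those whose whole response falls within the raised-dose period: 0 to 1.

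Patients on unchanged replacement are not in s, because they lose nothing from the response rate.

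| p | s | m | Observed | Loss (points) | Patients of 30 |
|---|---|---|---|---|---|
| any | any | 0 | p | 0 | 0 |
| 0.30 | 0.20 | 0.5 | 0.30 × (1 − 0.10) = 0.27 | 3 | 0.9 |
| 0.30 | 0.30 | 1 | 0.30 × (1 − 0.30) = 0.21 | 9 | 2.7 |
| 0.50 | 0.30 | 1 | 0.50 × (1 − 0.30) = 0.35 | 15 | 4.5 |

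For scale, 9 of 30 responders is 0.30 with an exact 95% confidence interval of 0.147 to 0.494. The mid-case loss is small against that width.

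**Step 4. Check what is not touched.** The modified RECIST 1.1 definitions in Appendix 2 rest on lesion disappearance or change in diameters and carry no steroid condition. The Section 4.1.2 primary endpoints, time to intracranial progression by modified RECIST 1.1 and overall survival, do not use the RANO-BM/iRANO response rule.

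**The case against.** A reader might infer that anyone on a non-neurologic steroid can never be scored as a brain responder, and that the intracranial response rate as a whole is biased low. The documents do not support this. The PR rule allows steroids at a stable or lower dose, so unchanged replacement costs CR only. Immune-event courses are tapered, and a lasting response can be scored later. One of the three versions of the endpoint has no steroid condition at all.

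A large bias also cannot be read from the 30% extracranial toxicity limit in Section 9.2. That is a stopping threshold, not a forecast, and it covers any related Grade 3 or higher event outside the CNS, immune or not. The 56% response rate in Section 1.2 belongs to a different regimen in melanoma.

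There is a fair case for the clause as well. Section 1.2 notes that corticosteroids matter for perilesional edema. A high dose given for pneumonitis may act on the brain too, so ignoring it could push response upward. Appendix 1 reproduces only selected sections of the source, so the full treatment of steroid indication cannot be seen. This stands, and it is a reason not to waive the condition for every non-CNS steroid. It does not justify counting physiological replacement, which exclusion 8 already treats as a separate case, or leaving the reference dose undefined.

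**Conclusion.** The point holds for the RANO-BM and iRANO versions of a secondary endpoint. Their CR rate can be understated, because no patient on replacement can reach CR. Their response rate can be understated to a lesser extent, through replacement started on study and doses raised for immune-related events, if the reference is baseline. For unchanged replacement the effect on the response rate is zero.

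The size cannot be derived from the documents. The 0 to 15 point range, and the mid-case of 3 points or 0.9 of 30 patients, depend wholly on the assumed p, s and m. If every affected responder is rescored after the taper (m = 0), the response rate loses nothing. Phase II has no response-rate hypothesis, but its stated purpose is to collect data for larger studies, so the definition should be settled before analysis.

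**What to change.** In Appendix 1:
- State that physiological replacement does not count as steroid use for CR or PR, in line with exclusion 8.
- Set the baseline dose as the reference for the PR steroid condition.
- Amend the sentence that calls the lesion-size change the only modification.

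Keep the strict criteria for all other steroids. In Section 9.3, add that RANO-BM and iRANO response will be reported with and without the steroid condition for steroids given for non-CNS indications. Section 7.0 already requires the indication of added or changed concomitant drugs on the eCRF. Section 6.2.7 does not name indication for drugs already in use, so it should be recorded for steroids taken at entry too.

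The cost is a few sentences, one extra tabulation, and a second stated departure from the published criteria. The change concerns scoring only; no change to steroid management is proposed.

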The RECIST criteria should be used to assess response to treatment. Only patients with measurable disease should be entered in the study. Measurable extracranial disease is defined as the presence of one lesion that can be accurately measured in at least one dimension (longest diameter to be recorded) as ≥ 2.0 cm with conventional techniques (or as ≥ 1.0 cm by spiral CT). Evaluable lesions should be followed for the assessment of response. Non-measurable lesions include bone lesions, ascites, pleural/pericardial effusion, lymphangitic carcinomatosis, abdominal masses that are not confirmed by CT, and cystic lesions. Disease progression and response evaluations for intracranial and extracranial disease will be determined according to the definitions established in the Response Evaluation Criteria in Solid Tumours (RECIST v1.1). Minor modifications will be applied to the assessment of intracranial lesions:

- General: target lesions should be representative of the subject's baseline tumor burden and should be selected based on their size (i.e. lesions with the longest diameter) and their suitability for accurate repeat assessment.
- Intracranial lesions: (the modifications to RECIST v1.1. impact the number and the minimal size of the target lesions selected at baseline) up to five lesions should be selected as target lesions; all brain lesions in excess of these five target lesions have to be regarded as non-target lesions. Measurable lesions are defined as those that can be accurately measured in at least one dimension with the longest diameter ≥ 5 mm when evaluated with contrast-enhanced MRI. Contrast-enhanced MRI is the only imaging modality accepted for assessment of intracranial lesions.
- Extracranial lesions: up to two lesions per organ representative of all involved organs should be selected as target lesions; the total number of target lesions should not exceed five and all lesions in excess of these five target lesions have to be regarded as non-target lesions.

Baseline Documentation of Intracranial Target and Non-Target Lesions

- All baseline lesion assessments must be performed within 28 days of the first dose of study treatment.

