- Measurable and non-measurable intracranial (i.e. brain parenchyma) lesions up to a maximum of 5 lesions should be identified as target lesions, and recorded and measured at baseline. These lesions should be selected on the basis of their size (lesions with the longest diameter) and their suitability for accurate repeated measurements (either by imaging techniques or clinically).
- Cystic lesions thought to represent cystic metastases should not be selected as target lesions when other suitable target lesions are available.
- Measurable intracranial lesions that have been previously irradiated and have not been shown to be progressing following irradiation should not be considered as target

Proprietary Information of MD Anderson

lesions. All other intracranial lesions should be identified as non-target and should also be recorded at baseline. Measurements of non-target lesions are not required, but the presence or absence of each should be noted throughout follow-up.

Baseline Documentation of Extracranial Target and Non-Target Lesions

- All baseline lesion assessments must be performed within 28 days of the first dose of study treatment.
- Lymph nodes that have a short axis of <10mm are considered non-pathological and should not be recorded or followed.
- Pathological lymph nodes with <15mm and ≥ 10 mm short axis are considered non measurable.
- Pathological lymph nodes with ≥ 15 mm short axis are considered measurable and can be selected as target lesions, however lymph nodes should not be selected as target lesions when other suitable target lesions are available.
- Measurable lesions up to a maximum of 2 lesions per organ and 5 lesions in total, representative of all involved extracranial organs, should be identified as target lesions, and recorded and measured at baseline. These lesions should be selected on the basis of their size (lesions with the longest diameter) and their suitability for accurate repeated measurements (either by imaging techniques or clinically).
- Cystic lesions thought to represent cystic metastases should not be selected as target lesions when other suitable target lesions are available.
- Measurable extracranial lesions that have been previously irradiated and have not been shown to be progressing following irradiation should not be considered as target lesions.
- Lytic bone lesions or mixed lytic-blastic lesions, with identifiable soft tissue components, that can be evaluated by CT or MRI can be considered measurable.

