- Bone scans, FDG-PET scans or X-rays are not considered adequate imaging techniques to measure bone lesions.
- All other lesions (or sites of disease, excluding the brain) should be identified as non-target and should also be recorded at baseline.
- Non-target lesions will be grouped by organ. Measurements of these lesions are not required, but the presence or absence of each should be noted throughout follow-up.

Overall Intracranial Response - Evaluation of Intracranial Target Lesions

Definitions for assessment of response for intracranial target lesion(s) are as follows:

- Complete Response (CR): Disappearance of all target lesions.
- Partial Response (PR): At least a 30% decrease in the sum of the diameters of target lesions, taking as a reference, the baseline sum of the diameters (e.g. percent change from baseline).
- Stable Disease (SD): Neither sufficient shrinkage to qualify for PR nor sufficient increase to qualify for progressive disease.

Proprietary Information of MD Anderson

- Progressive Disease (PD): At least a 20% increase in the sum of the diameters of target lesions, taking as a reference, the smallest sum of diameters recorded since the treatment started (e.g. percent change from nadir, where nadir is defined as the smallest sum of diameters recorded since treatment start). In addition, the sum must have an absolute increase from nadir of 5mm.
- Not Evaluable (NE): Cannot be classified by one of the four preceding definitions.

Note: If an intracranial target lesion disappears and reappears at a subsequent time point it should continue to be measured. The response at the time when the lesion reappears will depend upon the status of the other lesions. For example, if the disease had reached a CR status then PD would be documented at the time of reappearance. However, if the response status was PR or SD, the diameter of the reappearing lesion should be added to the remaining diameters and response determined based on percent change from baseline and percent change from nadir.

- Patients, who in the opinion of the treating physician investigator have had a substantial decline in their performance status and have clinical evidence of progressive disease may be classified as having progressive disease.

Appendix 2: Current National Cancer Institute Common Terminology Criteria for Adverse Events (NCI CTCAE Version 5.0)

Please use the following link to the NCI CTCAE website:

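### Appendix 2 contradicts itself on whether non-measurable brain lesions may be target lesions, so the primary progression endpoint can be read two ways

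*Combined protocol and SAP*

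**What the plan says.** All of the conflicting text is in Appendix 2 (RECIST v1.1 Criteria).

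- The intracranial modifications are introduced with the statement that "the modifications to RECIST v1.1. impact the number and the minimal size of the target lesions selected at baseline".
- Measurability in the brain is then defined: "Measurable lesions are defined as those that can be accurately measured in at least one dimension with the longest diameter ≥ 5 mm" on contrast-enhanced MRI. No other minimal size is given for brain lesions.
- On modality: "Contrast-enhanced MRI is the only imaging modality accepted for assessment of intracranial lesions".
- Under the baseline documentation of intracranial lesions, the instruction is: "Measurable and non-measurable intracranial (i.e. brain parenchyma) lesions up to a maximum of 5 lesions should be identified as target lesions". The same bullet says that these are recorded and measured, and chosen by size and by "their suitability for accurate repeated measurements (either by imaging techniques or clinically".
- The corresponding extracranial bullet begins: "Measurable lesions up to a maximum of 2 lesions per organ and 5 lesions in total".
- Intracranial progression on target lesions is "At least a 20% increase in the sum of the diameters of target lesions", taken from the smallest sum on treatment, together with an absolute rise of 5 mm.

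Sections 4.1.2 and 9.3.2 make time to intracranial progression by modified RECIST 1.1 a Phase II primary endpoint. Section 8.8 has the scans assessed locally, with up to five brain lesions followed. Section 8.1.4 bases treatment decisions on the same criteria.

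**The concern.** The appendix presents the 5 mm threshold as the minimal size of a target lesion, then tells the reader to take lesions below that threshold, or otherwise non-measurable, as targets. Both instructions cannot be followed. Target lesions are fixed at baseline, and every later percentage change is computed on their sum. Two local readers who each follow one of the two bullets correctly could therefore carry different sums for the same patient throughout follow-up. What is at stake is whether the response category, the progression call and the progression date are reproducible. The planned Phase II set is 30 patients, about 10 per tumour type (Section 9.2), so a few altered dates would show in the estimates.

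**Working it through.** The plan gives no figure to reproduce here. The check compares the texts and then uses a small arithmetic example.

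**1. Is there a reading that reconciles the two bullets?** The definition paragraph says the modifications concern the minimal size of targets, and 5 mm is the only size stated, so 5 mm must be that minimum. The baseline bullet admits non-measurable lesions as targets. No other text withdraws or limits those words. The surrounding provisions favour the 5 mm reading:
- the otherwise near-identical extracranial bullet is limited to measurable lesions;
- inclusion criterion 4 (Section 5.1) requires a measurable brain lesion of at least 0.5 cm;
- Section 6.2.8 makes brain response after radiosurgery depend on one measurable lesion remaining unirradiated.

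**2. Can the two rules give different calls on identical measurements?** Assume, for illustration only, a baseline of one 8 mm lesion and four 3 mm lesions.

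- Rule A (measurable only): baseline sum 8 mm.
- Rule B (all five): baseline sum 8 + 4 × 3 = 20 mm.

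The Appendix 2 thresholds are PR at a fall of at least 30% from baseline, and PD at a rise of at least 20% and 5 mm from nadir. The table compares one follow-up scan with baseline.

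| Measured at follow-up | Rule A | Rule B |
|---|---|---|
| 8 mm lesion now 5.6 mm; small lesions unchanged | 2.4/8 = 30% fall: PR | 2.4/20 = 12% fall: SD |
| 8 mm lesion unchanged; each small lesion +1.25 mm | 0% change: SD | 4 × 1.25 = 5 mm rise, 5/20 = 25%: PD |
| 8 mm lesion now 13 mm; each small lesion now 2 mm | 5 mm rise, 5/8 = 62.5%: PD | 13 + 8 = 21 mm; 1 mm rise, 1/20 = 5%: SD |

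The calls differ in all three cases without any measurement error, and for progression they differ in both directions. In the second case, Rule A leaves the small lesions as non-target. Growth there could still be judged progression, but by a different and unmeasured route.

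**3. Who is affected?** Only patients with fewer than five suitable measurable brain lesions who also have smaller or otherwise non-measurable ones. With five or more suitable lesions of at least 5 mm, the largest are chosen and the rules agree. The documents do not say how many of the 30 patients this is.

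**4. The second conflict in the same bullet.** Suitability may be judged by clinical measurement, yet MRI is the only modality accepted for intracranial lesions. Both statements cannot stand.

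**The case against.** The case for leaving the text alone has real content.

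- The bullet ranks lesions by size and by suitability for accurate repeat measurement, so a lesion that cannot be measured reliably should seldom be chosen. This stands as a limit, but it ranks candidates and does not exclude non-measurable ones.
- Five is a ceiling, not a quota. A reader might infer that every patient with fewer than five measurable lesions would have smaller ones added. The text does not support that: the patient must have such lesions, and they must pass the suitability test.
- Non-measurable is not only a matter of size. The appendix's general list of non-measurable lesions includes cystic ones, and a separate intracranial bullet restricts their use as targets.
- Progression by new lesions does not depend on target choice, and every patient has at least one measurable brain lesion at entry.
- Phase II is estimation only, with no efficacy test resting on the sum.

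A reader might also infer that small targets raise false progression by a calculable amount. The documents give no reading error and no lesion distribution, and a simple error model does not isolate lesion size. With independent error of standard deviation s on each of k targets, and the 5 mm condition binding, the chance of a false call at the first follow-up scan in stable disease is 1 − Φ(5 / (s√(2k))). Lesion size does not appear. Four 3 mm lesions plus one of 8 mm (20% of 20 mm = 4 mm, so the 5 mm condition binds) and five compliant 5 mm lesions (20% of 25 mm = 5 mm) both have k = 5 and give essentially the same answer. Comparing one target with five measures the number of targets, which the plan sets deliberately at up to five.

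Nor would the contradiction change how many patients are in the response-rate denominator. It changes each affected patient's baseline sum.

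**Conclusion.** The contradiction is real and unresolved in the current text, and it bears on a primary endpoint. For the patients described above, the two bullets can yield different target sums and hence different PR and PD calls and PD dates from the same scans. That conclusion needs no assumption about measurement error. It rests on the wording and on the target sum driving the calls. The lesion sizes in the example are assumed and show only that the calls can differ.

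The frequency and net effect on the estimates cannot be derived from the documents, so no percentage should be attached. The selection rule, the 5 mm absolute condition and progression by new lesions keep the effect limited. It should be corrected because the rule is wrong as written, not because a large bias has been shown.

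**What to change.** In the intracranial baseline bullet of Appendix 2, delete the words admitting non-measurable lesions, so that targets are measurable brain lesions (longest diameter at least 5 mm on contrast-enhanced MRI), up to five, and all others are recorded as non-target. In the same bullet, delete the option of clinical measurement, to agree with the MRI-only rule. When doing so, check that the intracranial bullet on cystic lesions still reads consistently with the general list of non-measurable disease.

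If smaller targets were in fact intended, the definition paragraph must say so and state how they are to be measured.

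The cost is a short wording change. No new data are needed, and smaller lesions stay under observation because the appendix already has non-target lesions recorded and their presence noted at follow-up. The downside is that some patients will have fewer target lesions.
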